#### Statistical analyses

The main outcome measures for the fMRI data will be brain activation defined by intensity and cluster size in response to performing elbow flexion and pinch. Second level analyses will be mixed models effects derived using FSL FLAME for within participants (pre to post intervention) as well as cross-sectional (non impaired vs. SCI-n; SCI-n vs. SCI+TT) individual models (with outlier de-weighting and standard settings). Separately, T1 and T2 voxelwise models will regress EMG pinch amplitude for that time-point onto brain data to examine neural correlates of our standard EMG outcome metric. The difference between T1 and T2 will be tested similarly (fMRI con images and EMG calculated as [pre-post/pre+post]) before regressing EMG onto voxelwise brain data.

*Pinch and elbow extension strength.* Pinch force is sampled simultaneously with the EMG data. A custom MATLAB program is used to locate the peak force that is maintained for at least 0.5 sec during the 10 sec trial. Mean pinch force is expressed in newtons (1 lb. = 4.454 N) before and after the training period.

*EMG amplitude analysis.* The EMG signals recorded during maximal pinch and maximal elbow flexion will be quantified by calculating a root-mean-square value over a 0.5 sec interval during peak force production. The ratio of the EMG amplitudes during maximal pinch to those during maximal elbow flexion will be calculated to normalize the EMG signals. During maximum pinch effort, the normalized EMG signals will be used to compare the amplitude of the transferred Br activation before and after the training program in each of the trials

and between participants. The normalized EMG activation will be expressed as a percent of the maximum voluntary contractions (MVC).

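### If the T1–T2 index is applied to signed fMRI contrast images, as the sentence most naturally reads, the brain–EMG change regression loses power in weakly activated voxels and reverses direction in deactivated ones

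*Combined protocol and SAP*

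**What the plan says.** All of the relevant text is in the Statistical analyses section of the combined protocol and SAP. The main fMRI outcome is "brain activation defined by intensity and cluster size in response to performing elbow flexion and pinch", analysed pre to post and between groups in FSL FLAME as "individual models (with outlier de-weighting and standard settings").

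A separate set of analyses links brain and muscle. At each time point, "T1 and T2 voxelwise models will regress EMG pinch amplitude for that time-point onto brain data". Change is then handled as follows: "The difference between T1 and T2 will be tested similarly (fMRI con images and EMG calculated as [pre-post/pre+post"), and this is done "before regressing EMG onto voxelwise brain data".

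Under EMG amplitude analysis, the EMG signal is "quantified by calculating a root-mean-square value over a 0.5 sec interval during peak force production" and normalised as the ratio of maximal pinch to maximal elbow flexion. It is therefore never negative.

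The plan does not define con images; contrast images are the plausible meaning. It states no mask, no restriction to positively activated voxels, no absolute value in the denominator and no rule for a sum near or below zero.

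**The concern.** The sentence makes the con images and EMG joint subjects of one formula. A normalised change index works for a non-negative quantity such as an RMS ratio. A contrast value is signed, so the denominator can be close to zero, giving extreme values, or negative, giving an index that points the opposite way to the signed change.

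This is the only planned analysis that relates change in brain activation to change in activation of the transferred muscle. If the index is used on the contrast images, true associations in weakly activated voxels would often be missed. One map could also show the same sign for a rise in one region and a fall in another.

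**Working it through.** **1. Inputs.** From the plan: the index, the voxelwise regression and the non-negative EMG scale. The plan gives no sample size, variance, pre/post correlation or effect size for this analysis, so there is no planned figure to reproduce. Every power figure below rests on assumed inputs.

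**2. Algebra (no assumptions).** Let I = (pre − post)/(pre + post).

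- If both values are non-negative and not both zero, |pre − post| ≤ pre + post, so I lies between −1 and +1. This is the EMG case.
- If the two values have opposite signs, |I| > 1, without limit as the sum approaches zero.
- If pre + post < 0, I has the opposite sign to pre − post at any sample size.

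| pre | post | pre − post | pre + post | I |
|---|---|---|---|---|
| 1.0 | 1.5 | −0.5 | 2.5 | −0.2 |
| −1.0 | −1.5 | 0.5 | −2.5 | −0.2 |
| −0.2 | 0.3 | −0.5 | 0.1 | −5 |
| 0.3 | −0.25 | 0.55 | 0.05 | 11 |
| −0.3 | 0.25 | −0.55 | −0.05 | 11 |

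Rows 1 and 2 are a rise and a fall with the same index. So are rows 5 and 4.

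**3. How often this happens.** Assume pre and post bivariate normal with mean m, SD 1 and correlation 0.5. The sum has mean 2m and variance 1 + 1 + 2(0.5) = 3, so P(sum < 0) = Φ(−2m/√3): 50%, 12.4%, about 1% and 0.03% at m = 0, 1, 2 and 3. The share of participants with |I| > 1 is 33%, 19%, 4% and 0.25%.

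**4. Power.** Simulation with 20,000 runs per cell, a single voxel and a two-sided 5% Pearson test. EMG change = r × (standardised contrast difference) + noise, with r = 0.7. The truth is linear in the difference, which favours the plain difference.

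| Group mean/SD | n=12, difference | n=12, index | n=20, difference | n=20, index |
|---|---|---|---|---|
| 0 | 78% | 10% | 96% | 10% |
| 1 | 78% | 21% | 96% | 24% |
| 2 | 78% | 55% | 96% | 70% |
| 3 | 78% | 72% | 96% | 91% |
| 4 | 78% | 75% | 96% | 94% |
| 5 | 78% | 76% | 96% | 95% |

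These count significance in either direction. At mean/SD 0 about half of the index's 10% is in the wrong direction.

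**5. Deactivated voxels, n=12.** At mean/SD −1, −2 and −3, the index is significant in the direction opposite to the contrast difference in 20%, 54% and 71% of runs. It is significant in the correct direction in 1.5% or fewer.

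**6. Type I error.** With EMG noise independent of the contrast, the index rejects in 4.8–5.2% of runs throughout.

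**7. Sensitivity, n=12, pre/post correlation 0.3 to 0.7.** With r = 0.7 the index gives about 10%, 20–24%, 51–58% and 70–72% at mean/SD 0, 1, 2 and 3. With r = 0.5 it gives 7–8%, 12–13%, 26–29% and 35–36%, against 40% for the difference.

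**8. De-weighting.** Ranks of the index, as a proxy at n=12, give 7%, 29% and 59% at mean/SD 0, 1 and 2. The result is still significant in the reversed direction in 59% and 66% of runs at −2 and −3.

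**9. A different data model.** Here EMG was positive and itself indexed, the between-person contrast SD was 0.5, the change SD was 0.5 plus noise, and the latent correlation was 0.6 (4,000 runs per scenario). At n=20 and mean contrast 2, 1, 0.5 and 0, power in the right direction was 0.75, 0.76, 0.74 and 0.75 with the difference, and 0.70, 0.39, 0.12 and 0.04 with the index. At −1 and −2 the index was significant in the wrong direction in 0.39 and 0.70 of runs. A Tukey biweight fit (300 runs) raised power at 1 and 0.5 to 0.60 and 0.33, but the wrong-direction share at −1 and −2 was still 0.64 and 0.67.

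**The case against.** **The reading.** The parenthesis is ambiguous. The con images may already be T1-versus-T2 contrasts, with the index describing EMG alone. The invalid step is then absent. This stands as a real limit. Even so, the formula lacks inner brackets (by operator order it is not the index at all), and the fMRI change measure needs to be stated.

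**Secondary analysis.** The regression explores neural correlates, and no efficacy conclusion depends on it. That is correct and limits the weight of the point.

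**Reversal as a matter of definition.** In a consistently deactivated voxel the index can be read as change in response magnitude: 1.0 to 1.5 and −1.0 to −1.5 are both 50% larger responses. That reading is coherent within one such voxel. It still leaves one map with two meanings under the same sign, and participants whose contrasts differ in sign are not comparable within a voxel.

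**Mask and de-weighting.** An activation mask would remove most of the reversal, but none is stated. De-weighting may carry over from the FLAME models, though the plan does not say so. At n=20 the rank proxy lifts power to 48% and 87% at mean/SD 1 and 2, from about 24% and 70%. It does not correct the reversal.

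**The remedy can lose.** If participants differ in overall signal gain (assumed log-SD 0.5, n=12), the plain difference has 67% power against 71%, 75% and 76% for the index at mean/SD 3, 4 and 5. The difference still does better at 1 and 2. This is a genuine cost in strongly activated voxels, and it does not make the index valid where contrasts are weak or negative.

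**Conclusion.** The concern holds, on the condition that the index is applied to the contrast images. Confidence is medium because the sentence admits the EMG-only reading.

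The reversal is algebraic and needs no assumed inputs beyond contrast values being signed. The power loss does depend on assumptions (normal contrasts, 12 or 20 participants, an association linear in the difference). Under them it is severe at mean/SD 0 to 1, substantial at 2, and 6 percentage points or less from 3 upward at n=12.

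The harm is missed associations and misread direction, not extra false positives. It is confined to the brain–EMG change regression. It should be fixed before analysis, because a rule followed as written could report the wrong direction of change.

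**What to change.** - For fMRI, use the within-participant difference between the T1 and T2 contrasts as the change measure, and say so.
- Restrict the normalised index to EMG and write it with explicit brackets, as (pre − post)/(pre + post) or the reverse.
- State one direction of subtraction and use it for both variables.
- State whether outlier de-weighting applies to this regression. Define con images and state any mask at the same time.

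The cost is one or two sentences of SAP wording and no new data. The downside is that fMRI change is no longer relative, so differences between participants in overall signal scale are not normalised; in strongly activated voxels the gain is small and can be negative. If a relative measure is wanted, a denominator of |pre| + |post| keeps the direction right. In the second simulation at n=20 it gave power of about 0.59–0.73, against 0.74–0.77 for the plain difference.

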## Purpose

The purpose of the study is to improve upper limb function in people who have suffered injuries to their cervical spinal cord and have lost hand function. Many individuals with tetraplegia choose to undergo surgery, such as muscle-tendon transfers that restore function to their paralyzed upper limbs. In this study we will compare their ability to produce pinch force between the thumb and index finger before and after participating in a home exercise program. The exercises are designed to improve the strength and performance of the transferred muscle and also the muscles that are important to stabilize proximal joints.

The investigators anticipate the study will inform new postoperative treatment protocols designed to re-educate the transferred muscle in its new functional role. The objective is to determine if training to improve muscle strength and coordination will improve the ability to increase pinch strength after tendon transfer to restore pinch strength. Restoration of upper extremity function is rated among the highest priorities for individuals with tetraplegia. Use of the upper extremity is critical to functional independence, quality of life, ability to participate in society, and reduced burden of care.

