## Study Procedures

**Recruitment and screening:** We will invite individuals to participate if they have a SCI resulting in tetraplegia with a previous tendon transfer surgery to restore their ability to pinch and grasp. Individuals with tetraplegia will be recruited from the Upper Extremity Clinics for Spinal Cord Injury at the VA Palo Alto Health Care System, Stanford University Hospital Clinics, and Valley Medical Center in San Jose, CA. A hand surgeon and the PI will attend all of the clinics. A letter may be sent to individuals who have expressed interest in previous studies to be contacted for participation in any new studies.

Participants will be scheduled for 1 to 2 test sessions in the Laboratory for Upper Extremity Research in the SCI Center (UE Lab). In the first session a set of measurements will be taken for baseline data of strength, muscle activation, and ability to perform functional pinch tasks. An fMRI study will be included in the first session. Each participant with tendon transfer procedures will be given a set of exercise equipment to take home. The equipment will include a set of weights for resistance exercise (i.e. lifting weights), a digital pinch meter for biofeedback of the pinch force, a table-top device that is used to provide target locations the participants reach for and to practice pinch (using variable resistance pinch pins) in locations that simulate the actual functional pinch tasks, and a task board with tasks that require pinch strength (ex: key, atm card, zipper).

The participants will get verbal and written instructions about how to use the equipment and a log-book to record their practice sessions. They will be instructed to practice the exercises for 10 weeks. A second appointment in the UE Lab will be scheduled to measure any changes in pinch function after the exercise program. A set of measurements that are identical to the baseline data set will be obtained, including the fMRI study.

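### Is the pre/post analysis of pinch force and EMG left undefined, and does the pound-to-newton factor matter?

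*Combined protocol and SAP*

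**What the plan says.** All references are to the combined protocol and SAP.

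- **Purpose.** The study question is a before/after comparison: "we will compare their ability to produce pinch force between the thumb and index finger before and after" the home program. The objective is stated in the same terms: "The objective is to determine if training to improve muscle strength and coordination will improve the ability to increase pinch strength after tendon transfer".
- **Study Procedures.** At the second laboratory visit, after 10 weeks, "A set of measurements that are identical to the baseline data set will be obtained". Each participant therefore supplies a pair of values.
- **Statistical analyses, pinch strength.** Peak force held for at least 0.5 s is located within a 10 s trial. The paragraph then ends: "Mean pinch force is expressed in newtons (1 lb. = 4.454 N) before and after the training period".
- **Statistical analyses, EMG.** Normalised signals are used to "compare the amplitude of the transferred Br activation before and after the training program in each of the trials", and the sentence goes on to add a comparison between participants.
- **Statistical analyses, fMRI.** The second-level models are "derived using FSL FLAME for within participants (pre to post intervention") and also cross-sectional. Separate voxelwise models at T1 and at T2 use the pinch EMG amplitude of that time point. The T1 to T2 difference is then to be tested in a similar way, with "EMG calculated as [pre-post/pre+post]) before regressing EMG onto voxelwise brain data".

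**The concern.** Three things catch the eye.

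1. The outcome that the Purpose puts first has the thinnest analysis text. Imaging has a named within-participant model; pinch force has two means. The text does not say whether the mean is over a participant's trials or over participants, and two means alone carry no precision for the change.
2. The EMG sentence speaks of a comparison in each trial. Read literally, it would allow trials to be treated as independent observations or tested one at a time. The first understates the standard error when a participant's trials resemble each other; the second multiplies the chances of a false positive.
3. The printed pound-to-newton factor does not agree with the definition of the units.

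If the first two reflected what will be done, the main question could be answered without an interval, and an EMG effect could be declared on too little evidence.

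**Working it through.** **Conversion factor.** This is the only figure in the plan that can be recomputed here. From the unit definitions (not from the documents), 1 lbf = 0.45359237 kg × 9.80665 m/s² = 4.44822 N. The plan prints 4.454.

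- Relative error: 4.454 / 4.44822 − 1 = 0.13%.
- At 5 lb: 22.27 N against 22.24 N. At 10 lb: 10 × (4.454 − 4.44822) = 0.058 N.
- Rounded constants give 0.454 × 9.81 = 4.4537, so rounding is a plausible source.
- In a paired test, t = mean(d) / (SD(d)/√n). A common factor multiplies numerator and denominator and cancels. In an illustrative data set of 10 pairs, t = 3.786 and p = 0.0043 under both factors. Percent change is likewise unaffected.

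**Pinch force.** The Purpose says before and after are compared. Study Procedures says the same measurements are taken twice in the same people. The force paragraph says values are reported before and after. Together these describe paired data and a paired contrast; what is missing is the name of the test and the interval. The mean comes directly after the rule for finding the peak within a trial, so averaging a participant's trials is the natural reading, though it is not stated.

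The precision that two means do not show is the 95% half-width for a mean change, t(0.975, n−1)/√n in units of the SD of change. The documents give no n; for assumed values:

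- n = 8: 2.365/√8 = 0.84
- n = 12: 2.201/√12 = 0.64
- n = 20: 2.093/√20 = 0.47

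These widths come from the number of participants. Writing the interval into the plan would not alter them.

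**EMG unit of analysis.** All inputs are assumed: 8 to 20 participants, k = 2 to 5 trials, a two-sided 5% test, and within-participant correlation ρ of the trial-level changes.

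- *Trials pooled as independent.* The variance of the mean change is understated by 1 + (k−1)ρ. For k = 2 and ρ = 0.3 this is 1.3; 1.96/√1.3 = 1.72, a true error rate of about 8.6%. Simulation gives 8.5% there. It gives 12% to 24% for k = 3 and 19% to 37% for k = 5, with ρ from 0.3 to 0.8. At ρ = 0 it is about 5%, and at ρ = 0.1 about 6% to 10%.
- *Each trial tested separately.* Each test holds about 5%. The chance of at least one false positive runs from 7.8% (k = 2, ρ = 0.8) to 22% (k = 5, ρ = 0.3).
- *Trials averaged within participant.* About 5% throughout.

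The question is then which of these the plan implies. No sentence says that trials are pooled or that each is tested. The voxelwise models use the EMG amplitude of a time point as a regressor in group-level brain models, and such a regressor normally carries one value per participant per time point. The change index also presupposes a single pre and a single post value. Both point to a participant-level summary.

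**The case for a change.** The strongest case for a change is that an unstated rule is an open choice. Until the test, the summary over trials and the unit are written down, they can be settled after the data are seen, and they concern the outcome in the Purpose. The same section shows that the authors could name a within-participant model, because they did so for imaging. The plural trials makes repeats the natural reading, and the added comparison between participants does not make the participant the unit for the before/after contrast. The cure would cost a few sentences and no data.

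Much of this is factually right. No interval or test is named for the change in pinch force, and the rule for combining EMG trials is absent. What does not carry is the step from silence to a faulty analysis. The inflated error rates belong to analyses that the plan does not state, and every input to them is assumed. The statement that the T1 to T2 difference will be tested is ambiguous: it may refer only to the voxelwise regression, or it may include a test of the EMG change. It cannot be taken as proof that EMG change goes untested, and it does not speak to pinch force either way.

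**Conclusion.** The omissions are real, but they are details that the design itself settles. Identical measurements taken twice in the same people, with a stated before/after question, lead an analyst to one value per participant per session and a paired contrast with its interval. For EMG, the wording is loose but contains no commitment to trial-level inference, and the imaging models point to participant-level values. Averaged in that way, the error rate stays at about 5% in every scenario tried.

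The figures of about 8.5% to 37% would matter only if trials were pooled as independent and their changes were correlated within participant. The documents neither say the first nor give the numbers needed to size the second.

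The conversion factor is a clerical slip of 0.13%. It shifts reported newton values slightly, if recordings are converted from pounds at all, and cannot alter a paired test, a percent change or a conclusion. No change to the plan is called for.

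This rests on one assumption: that the analysts follow the pairing that the Purpose and Study Procedures set up. A report that treated trials as independent would be open to criticism as an analysis, whatever the plan had said.

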**Home Exercise Training Program:** Participants will be instructed to use resistance exercises to strengthen elbow flexor and extensor muscle groups. The exercises should be done 3 times per week and should take about 30 minutes to complete. They will be instructed to do the strengthening exercises and practice pinching using the table-top device and the task board to practice producing pinch force in specific locations that simulate the position of an ATM machine, horizontal and vertical zippers, using a fork, electric plug, remote control, and a key. All of the instructions for performing the exercises will be provided and each participant will practice the home exercises at the first test session. The participants will receive a log- book to document their participation in the exercise program. The participants will not be able to keep the exercise weights, brace, pinch meter, or table-top device. They will be used for other participants who are enrolled in the study over the next 2 years. The equipment in the exercise kit will be cleaned with anti-bacterial soap after use by individual participants.

**Measurement of muscle structure and function:** Quantitative measurements of UE impairment will be recorded in the UE Lab. These measures include: muscle activation patterns with surface and fine- wire electrodes; and muscle strength using commercially available force transducers. A standardized test (Canadian Occupational

Performance Measure) designed to detect self-perceived changes in performance over time will be administered by the examiner. In the test, participants will be asked to identify daily activities they want to be able to do and those which are difficult to complete to your satisfaction. The questions will relate to self-care, productivity, and leisure activities. This survey will be completed by the examiner before and after the training program.

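### Does the slightly wrong pound-to-newton factor (4.454 rather than 4.448) distort the pinch-force results?

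*Combined protocol and SAP*

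**What the plan says.** The Purpose section makes pinch force a central measurement: "we will compare their ability to produce pinch force between the thumb and index finger before and after participating in a home exercise program". Under Study Procedures, in the paragraph on measuring muscle structure and function, the instruments are described only as measuring "muscle strength using commercially available force transducers". The paragraph on pinch and elbow extension strength under Statistical analyses says "Pinch force is sampled simultaneously with the EMG data", and then "A custom MATLAB program is used to locate the peak force that is maintained for at least 0.5 sec during the 10 sec trial". It ends with the reporting unit and the factor at issue: "Mean pinch force is expressed in newtons (1 lb. = 4.454 N) before and after the training period".

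This is the only unit conversion in the documents. Nothing elsewhere corrects it. Nothing states whether the laboratory transducers, or the digital pinch meter in the home kit, record in pounds or in newtons.

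**The concern.** The factor is given to three decimals, so it reads as an exact equivalence, yet it is not the pound-force rounded to three decimals. It stands in the sentence that fixes how a central outcome is reported, where a programmer or reader might copy it. If raw forces are in pounds and are multiplied by this constant, every pinch force in newtons, and the size of every mean change in newtons, would be inflated. A wrong constant in the handling of a main outcome deserves a check of whether the pre-to-post comparison could be affected.

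**Working it through.** **Inputs.** The stated factor is 4.454 N per lb (Statistical analyses, strength paragraph). The unit definition is 1 lbf = 0.45359237 kg × 9.80665 m/s². The documents give no expected pinch force, so the pound values below are assumptions chosen to show a range.

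**Step 1: can the stated figure be reproduced?** Not from the definition:

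0.45359237 × 9.80665 = 4.44822 N, which is 4.448 to three decimals.

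It can be reached with rounded or non-standard inputs:

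- 0.454 × 9.81 = 4.45374, which rounds to 4.454
- 0.45359237 × 9.82 = 4.45428, which also rounds to 4.454

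Either is a possible origin. The documents do not say which, and neither makes the equivalence correct. To two decimals the stated and defined values agree at 4.45.

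**Step 2: size of the error.**

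- Absolute: 4.454 − 4.44822 = 0.00578 N per lb
- Relative: 4.454 / 4.44822 − 1 = 0.0013, or 0.13%

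**Step 3: effect on force values, if pounds are converted with 4.454.**

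| Assumed force | With 4.454 | With 4.44822 | Excess |
|---|---|---|---|
| 2 lb | 8.908 N | 8.896 N | 0.012 N |
| 5 lb | 22.270 N | 22.241 N | 0.029 N |
| 10 lb | 44.540 N | 44.482 N | 0.058 N |
| 20 lb | 89.080 N | 88.964 N | 0.116 N |

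If the transducers are calibrated in newtons, the last column is zero throughout.

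**Step 4: effect on the pre-to-post comparison.** Let x and y be one participant's force in pounds before and after training, and c the factor used at both visits.

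- Change in newtons: cy − cx = c(y − x). Its size scales with c, so a gain and a loss are both exaggerated by 0.13%. The sign never changes.
- Percent change: (cy − cx)/(cx) = (y − x)/x. The factor cancels.
- Test statistic: the strength paragraph names no test. For a paired t, the mean difference and its standard error are both multiplied by c, so t and its p-value are unchanged. Signed ranks of the differences are also unchanged. Any scale-invariant test behaves the same way.

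**Step 5: other outcomes.**

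- The EMG measure is a ratio of two EMG amplitudes. Force serves only to locate the 0.5 sec window around the peak, and multiplying a force trace by a positive constant does not move its peak.
- The fMRI outcomes are activation intensity and cluster size. The voxelwise models use EMG, not force.
- The documents give no responder cut-off in newtons and no sample size, power or effect size that uses the factor.

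**Step 6: the one way the cancellation fails.** If one visit were converted with 4.454 and the other with the defined value, an unchanged force would show a spurious change of 0.13%: 0.029 N at an assumed 5 lb, 0.058 N at 10 lb. Nothing in the documents suggests mixed use, since a single factor is printed for both time points.

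**The case for a change.** The best case for a change is that the constant is wrong by definition, that it sits in the sentence defining how a central outcome is expressed, and that correcting one number costs almost nothing. Naming the transducers' native unit would also settle whether any conversion takes place. A further risk is that someone corrects the factor for some records only, so that the error no longer cancels between visits.

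The first point stands: 4.454 is not the pound-force, and no other part of the documents puts it right. The rest does not amount to a defect in the plan. The reporting unit is already fixed as newtons, so the missing native unit is a detail that the laboratory and its MATLAB program must already settle in order to produce a force value. Mixed use of factors is hypothetical and would itself produce only the 0.13% artefact. That a correction is cheap shows it would do no harm. It does not show that the study would gain anything in design, analysis or interpretation.

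**Conclusion.** The printed factor is a clerical slip: 4.454 N against 4.448 N per pound, 0.13% too high. No change to the plan follows. At worst, absolute pinch forces and the size of mean changes are overstated by 0.13%, about 0.01 to 0.06 N for assumed forces of 2 to 10 lb. At best, with transducers reading in newtons, nothing is affected. Percent change, any scale-invariant comparison before and after training, the normalized EMG and the fMRI results are the same under either value.

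This rests on two assumptions: that one factor is used at both visits, and that no decision depends on an absolute newton threshold. The documents print one factor and set no threshold. An analyst who uses the standard equivalence when converting, or a copy editor who corrects the figure, would leave every conclusion where it was.
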